7.3 TRIAL GOVERNANCE AND OVERSIGHT

7.3.1 Executive Committee

The executive committee (EC) provides scientific leadership of the VICTORIA study. As described in the EC charter, the EC consists of the following individuals:

- Executive Committee Chair
- Co-principal investigators
- Independent academic scientific leaders
- Clinical leaders from the Canadian VIGOUR Centre
- Clinical leaders from the Duke Clinical Research Institute
- Sponsor Senior Management

The EC will be responsible for all scientific aspects of the study, maintaining effective and independent scientific oversight, and will ensure that study execution and management are of the highest quality. The EC will convene regularly to discuss and report on ongoing supervision of the study. The EC serves as the publications committee and is responsible for oversight of all public and scientific communications and publications. On decisions regarding early termination of the trial, the EC will receive recommendations from the DSMB and then the EC will provide recommendations to the Sponsor, who has final decision making rights.

7.3.2 National Leader Committee

The primary role of the National Leader Committee is to serve as the interface between the Executive Committee and the study sites for the VICTORIA trial and to facilitate the progress of the study at the regional level. The National Leader Committee is composed of Country Leads selected by the Executive Committee from investigators in each country with appropriate clinical trial experience. National Leader Committee members should participate with their local site in VICTORIA to ensure adequate direct experience with the trial.

7.3.3 Data Safety Monitoring Board

To supplement the routine trial monitoring outlined in this protocol, an external Data Safety Monitoring Board (DSMB) will monitor the interim data from this trial. The voting members of the committee are external to the Sponsor. The members of the DSMB must not be involved with the trial in any other way (e.g., they cannot be trial investigators) and must have no competing interests that could affect their roles with respect to the trial.

The DSMB will make recommendations to the EC regarding steps to ensure both subject safety and the continued ethical integrity of the trial. Also, the DSMB will review interim trial results, consider the overall risk and benefit to trial participants (see Section 8.7 - Interim Analyses) and recommend to the EC if the trial should continue in accordance with the protocol.

Specific details regarding composition, responsibilities, and governance, including the roles and responsibilities of the various members and the Sponsor; meeting facilitation; the trial governance structure; and requirements for and proper documentation of DSMB reports, minutes, and recommendations will be described in a separate charter that is reviewed and approved by the DSMB. The DSMB will monitor the trial at an appropriate frequency, as described in the detailed DSMB charter. The DSMB will also make recommendations to the Sponsor regarding steps to ensure both subject safety and the continued ethical integrity of the trial.

A DSMB recommendation will be communicated to the Sponsor as agreed to in the Collaboration agreement.

7.3.4 Clinical Events Committee

A Clinical Events Committee (CEC) will evaluate the following events for the purposes of confirming them according to the criteria in Section 8.0 – Statistical Analysis Plan, as well as evaluating the presence of confounding factors.

- 1) Death
- 2) Cardiovascular Hospitalizations
- 3) Urgent Heart Failure Visit

All personnel involved in the adjudication process will remain blinded to treatment allocation throughout the trial. Specific details regarding endpoint definitions can be found in the CEC Charter.

8.0 STATISTICAL ANALYSIS PLAN

This section outlines the statistical analysis strategy and procedures for the study. If, after the study has begun, but prior to any unblinding, changes are made to primary and/or secondary hypotheses, or the statistical methods related to those hypotheses, then the protocol will be amended (consistent with ICH Guideline E-9). Changes to exploratory or other non-confirmatory analyses made after the protocol has been finalized, but prior to unblinding, will be documented in a supplemental SAP (sSAP) and referenced in the Clinical Study Report (CSR) for the study. Post hoc exploratory analyses will be clearly identified in the CSR. PK/PD endpoints and analysis approaches will be described in a separate detailed PK/PD evaluation and analysis plan.

8.1 Statistical Analysis Plan Summary

Key elements of the statistical analysis plan are summarized below; the comprehensive plan is provided in Sections 8.2 to 8.10.

Study Design Overview	A randomized parallel-group, placebo-controlled, double-blind, event-driven, multi-center phase III clinical outcome trial of efficacy and safety of the oral sGC stimulator Vericiguat in subjects with heart failure with reduced ejection fraction (HFrEF)
Treatment Assignment	
Randomization method: Treatment allocation/randomization will occur centrally using an interactive voice response system / integrated web response system (IVRS/IWRS). There are 2 treatment arms. Subjects will be assigned randomly in a 1:1 ratio to MK-1242 (vericiguat) or matching placebo, respectively.
 
Stratification method: Treatment allocation/randomization will be stratified in the following strata:
 
 Eastern Europe plus Israel and South Africa Western Europe North America (Black) North America (Non-black) Latin and South America Asia Pacific (including Australia)
Analysis Populations	
Primary Efficacy Analysis: ITT population.
 
Secondary Efficacy Analysis: ITT population
 
Safety: All subjects as treated (ASaT)

Primary Endpoint(s)	Time to the first occurrence of the composite endpoint of CV death or HF hospitalization.
Secondary Endpoints	
Time to CV death
 
Time to first HF hospitalization
 
Time to total HF hospitalizations (first and recurrent)
 
Time to the composite of all-cause mortality or HF hospitalization
 
Time to all-cause mortality

Statistical Methods for Key Efficacy	
The analysis of the primary endpoint will be performed with a one-sided log-rank test, stratified by the same strata that are considered for randomization, to test if the time to first composite of CV death or HF hospitalization is prolonged in the vericiguat treatment group compared to placebo.
 
The same one-sided stratified log-rank test will be used to test if the time-to first HF hospitalization, time-to CV death, time-to all-cause mortality, and time to the composite of all-cause mortality and HF hospitalization is prolonged in the vericiguat treatment group compared to placebo.
 
The time-to total HF hospitalization will be tested with an Andersen-Gill model to compare the vericiguat treatment group to placebo.
 
The overall study-wise type I error rate will be controlled at 0.025 (one-sided).

Statistical Methods for Key Safety Analyses	95% confidence intervals (Tier 1 and Tier 2) will be provided for between-treatment differences in the percentage of subjects with events; these analyses will be performed using the unstratified Miettinen and Nurminen method. In addition, p-values will be provided for Tier 1 safety endpoints.
Interim Analyses	
One interim analysis for efficacy is planned at the time when approximately 75% (587) of the planned number of CV death events are observed and the median follow up time is at least 10 months. At the interim analysis, both the primary composite endpoint of time to CV death or HF hospitalization and its component time to CV death will be tested. The study can only be terminated early for success if both the primary endpoint and the CV death component are statistically significant based on the nominal significance level used for the interim analysis.
 
At the same time as the interim analysis for efficacy, a futility analysis will be performed with the option to terminate the study early if it is determined at the time of analysis that the study is unlikely to demonstrate the efficacy of vericiguat on the primary endpoint and CV death.
 
An unblinded Data Safety Monitoring Board (DSMB) will assess the unblinded results of the interim analysis and may recommend early study termination for overwhelming efficacy or futility.

Multiplicity	The secondary endpoints will be separated into two families. The first family consists of the components of the primary endpoint, CV death and HF hospitalization, and the second family consists of total HF hospitalization, composite of all-cause mortality or HF hospitalization, and all-cause mortality. CV death and HF hospitalization will be tested only if the primary composite endpoint is significant and will be tested in parallel with multiplicity adjusted for the interim analysis only. Other secondary endpoints will be tested using a hierarchical testing approach.
Sample Size and Power	The sample size calculation is driven by the CV death component of the composite primary endpoint. For the CV death component, the expected event rate in the comparator group after 12 months is 11%. The relative risk reduction with vericiguat is assumed to be 20% for both CV death and primary endpoint, relating to a HR of 0.8. Using the log-rank test, a sample size of 4872 subjects and a total of 782 CV deaths will be required to achieve 80% power. With this sample size, it is expected that 1561 subjects with a primary endpoint event will be observed and there will approximately be 98% power for primary hypothesis testing. However, since the study duration will be driven by the number of CV death events, the expected number of primary endpoint events may differ from the actual observed number of primary endpoint events.

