with t denoting the percentage of information included at the respective interim analysis.

With this alpha spending approach, the nominal significance level will be approximately 0.0049 (one-sided) at the interim analysis and 0.0242 at the final analysis, respectively. This testing approach controls the one-sided alpha between the efficacy interim analysis and final analysis at 0.025. The corresponding observed hazard ratio for the stopping boundary is approximately 0.81 for CV death at the efficacy interim analysis.

The actual α to be spent at the efficacy interim analysis and final analysis will be precisely determined using the number of actually observed primary outcome events and the alpha spending function defined as above.

At the time of the interim analysis, approximately 587 CV death events and approximately 1171 (may vary depending on the actual event rate) primary endpoint events are expected. A one-sided stratified log-rank test will be used to assess if vericiguat prolongs the time to primary composite endpoint event compared with placebo. The same nominal significance level as used for the primary composite endpoint will also be used for the analysis of the CV death component.

If the study can be stopped early for success, the nominal one-sided significance level of approximately 0.0049 for the primary endpoint and CV death will be applied to other secondary endpoints as well.

If the study cannot be stopped early for success, the CV death component will be analyzed at the final analysis time point as one of the secondary endpoints.

An unblinded DSMB will assess the results of the interim analysis and may recommend early study termination if the interim analysis shows clear and consistent benefit of vericiguat as guided by the above described alpha-spending approach.

If the DSMB recommendation leads to termination of the study at the interim analysis due to efficacy, all subjects will be called in to their final visit. The complete analysis will be based on the entire data collected until the study completion, i.e. it will also include data collected after the cut-off for the interim analysis.

Table 9 summarizes the timing, number of events, endpoint, and the efficacy and futility bounds at each of the interim analysis and at the final analysis.

Table 9 Summaries of the Interim and Final Analyses

Analysis	Key Endpoint(s)	Target Number of Events	Anticipated Time From Study Start	Statistical Testing Criteria

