Futility Interim Analysis	Primary Endpoint Time to CV Death	587 CV Death [†] (75% of planned number of events)	Month 33 [†]	A point estimate of HR>0.95 for the primary endpoint and a point estimate of HR>1.0 for CV death for futility
Efficacy Interim Analysis	Primary Endpoint, Time to CV Death	587 CV Deaths [†] (75% of planned number of events)	Month 33 [†]	P<0.0049 (one-sided) on both endpoints for efficacy, corresponding to an observed HR<0.81 for Time to CV Death
Final Analysis	Primary Endpoint, Secondary Endpoints	782 CV deaths [†]	Month 39 [†]	P<0.0242 (one-sided) for statistical significance, using the pre-specified multiplicity adjustment approach (Section 8.8)

[†]Median follow up time of 10 months are also required.

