8.8 Multiplicity Adjustment

The study-wise one-sided alpha level will be controlled at 0.025 for the test of the primary endpoint. Multiplicity due to the interim analysis at 75% of planned CV death events will be controlled using a Hwang, Shih and DeCani ($\gamma=6.5$) alpha spending function as described in section 8.7.

The secondary endpoints will be separated into two families. The first family consists of the components of the primary endpoint, time to CV death and time to first HF hospitalization.

The second family will consist of the endpoints of time to total HF hospitalization, time to all-cause mortality, and time to first occurrence of composite of HF hospitalization or all-cause mortality. The endpoints from the second family will be tested hierarchically and at the same time be adjusted for the interim analysis, thereby maintaining the study-wise alpha level. These secondary endpoints will only be tested if both the primary composite endpoint and CV death are significant at the interim analysis, or if the primary composite endpoint alone is significant at the final analysis. Total HF hospitalization will be tested first, and only if this is significant, the composite of all-cause mortality and HF hospitalization will be tested afterwards. All-cause mortality will be tested only if both of the above endpoints are tested significant (see Figure 2 for the procedure at the final analysis).

At the interim analysis, if the study is stopped early for efficacy due to success on the primary composite endpoint and separately the CV death component, then the HF hospitalization component will be tested at the same alpha level as the CV death component. In addition, the family of secondary endpoints will be tested in a sequential manner using the same alpha as the primary composite endpoint.

[figure not shown]

Figure 2 Testing of Primary and Secondary Endpoints

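### The 0.025 described as study-wise covers the primary endpoint and each secondary family separately, not both secondary families together

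*Combined protocol and SAP*

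**What the plan says.** - **Section 8.1, key efficacy methods.** After describing the tests for the primary and the five secondary endpoints, the summary says: "The overall study-wise type I error rate will be controlled at 0.025 (one-sided"). It names no endpoint.
- **Section 8.1, Multiplicity row.** CV death and first HF hospitalization (first family) are tested only after a significant primary, and then "will be tested in parallel with multiplicity adjusted for the interim analysis only".
- **Section 8.8, opening.** "The study-wise one-sided alpha level will be controlled at 0.025 for the test of the primary endpoint".
- **Section 8.8, second family.** Total HF hospitalization, then all-cause mortality or HF hospitalization, then all-cause mortality are "tested hierarchically and at the same time be adjusted for the interim analysis, thereby maintaining the study-wise alpha level". At the final analysis this family opens "or if the primary composite endpoint alone is significant at the final analysis".
- **Table 9, final analysis.** "P<0.0242 (one-sided) for statistical significance, using the pre-specified multiplicity adjustment approach (Section 8.8").
- **Interim stop for efficacy.** Section 8.7.2 says the level of about 0.0049 "for the primary endpoint and CV death will be applied to other secondary endpoints as well". Section 8.8 adds that "the family of secondary endpoints will be tested in a sequential manner using the same alpha as the primary composite endpoint".

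The text nowhere divides alpha between the two families or makes one depend on the other. Figure 2, to which Section 8.8 refers for the final analysis, was not available in the copy reviewed.

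**The concern.** The statement in Section 8.1 and the second-family sentence in Section 8.8 can both be read as control over every confirmatory test. The procedure in the text does not give that. Each family is protected by the primary gate and by its own structure, but each then has the full level.

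Two true null hypotheses can therefore sit in different families, each tested at 0.0242:

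- **Benefit on HF hospitalization only.** The primary, total HF hospitalization and the all-cause mortality or HF hospitalization composite can all succeed. CV death (first family) and all-cause mortality (second family) are both null.
- **Benefit on CV death only.** First HF hospitalization (first family) and total HF hospitalization (second family) are both null.

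Section 3.2 gives all five secondary endpoints formal superiority hypotheses. A reader relying on Section 8.1 would take a mortality claim as jointly protected at 0.025. The first configuration, where the mortality endpoints are the exposed pair, is the one in which that fails most clearly.

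**Working it through.** **1. Reproduce the plan's levels.** With the spending function of Section 8.7.2, t = 0.75 and γ = −6.5:

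0.025 × (1 − e^4.875) / (1 − e^6.5) = 0.0049 at the interim.

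The final level solves P(Z₁ > 2.583 or Z₂ > c) = 0.025 with correlation √0.75. This gives c = 1.974, or 0.0242. Both match the plan. (The printed formula needs γ = −6.5; the γ = 6.5 printed would spend 0.0248 at the interim. That is a separate point.)

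**2. Two nulls with the gates open.** For two true nulls tested at 0.0242 with correlation ρ between the statistics, P(at least one false claim) = 1 − Φ₂(1.974, 1.974; ρ).

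| ρ | P(at least one) |
|---|---|
| 0.96 | 3.1% |
| 0.92 | 3.3% |
| 0.87 | 3.5% |
| 0 (ceiling) | 4.8% |

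The simulated correlation of CV death with all-cause mortality is 0.87 to 0.96 for non-CV death at 4% to 1% per year.

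**3. Full procedure by simulation.** Inputs from Section 8.9: 4872 subjects 1:1, placebo 12-month rates of 11% (CV death) and 23% (composite), 2% per year lost to follow-up, 10% per year stopping treatment and moving to the placebo hazard. Levels are 0.0049 and 0.0242, with the gates and hierarchy as written. Hazard ratios below are on-treatment values. Assumed, because the documents do not give them: gamma frailty on HF hospitalization, non-CV death of 2% per year (1% and 4% as sensitivity), independent CV death and HF hospitalization hazards, unstratified tests.

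- *Simulation A* analyses at months 33 and 39 and uses frailty variance 0.5, 1 and 2. Simulated correlations and means feed a multivariate normal.
- *Simulation B* analyses at 587 and 782 CV deaths, runs the whole procedure on subject-level data, and mostly uses frailty variance 1.

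Check with HR 0.80 on both components. A gives 758–760 CV deaths, 1474–1506 composite events and median follow-up of 530 days (plan: 782, 1561, 532). B gives power of 79.3% for CV death and 96.3% for the primary (plan: 80%, 98%).

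**4. Chance of at least one false secondary claim.**

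| True effect | A, final look only | A, interim stop always taken | B, interim stop always taken |
|---|---|---|---|
| HF hospitalization only, HR 0.90 | 1.8–2.0% | – | – |
| HF hospitalization only, HR 0.85 | 2.5–2.7% | – | – |
| HF hospitalization only, HR 0.80 | 2.9–3.1% | 2.9–3.3%* | 3.2% |
| HF hospitalization only, HR 0.70 | – | – | 3.3% |
| HF hospitalization only, HR 0.60 | – | – | 3.2–3.7%* |
| CV death only, HR 0.90 | 2.4–2.6% | – | – |
| CV death only, HR 0.85 | 3.0–3.2% | 2.4–2.6% | – |
| CV death only, HR 0.80 | 3.2–3.5% | 2.1–2.3% | 2.5% |
| CV death only, HR 0.70 | – | – | 1.0% |

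*Range includes non-CV death at 1% and 4% per year.

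For CV death only at HR 0.70, B without an interim stop gives 3.6–3.7%. With no effect on either component, B gives 2.53% for any false claim (standard error 0.11 points).

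**5. Where the excess arises.** In B, with benefit on HF hospitalization only at HR 0.80, CV death alone is falsely claimed in 2.50% of trials. Adding all-cause mortality raises this to 3.18%. The extra 0.68 points come from the second family opening beside the first. An interim stop occurs in about 0.4% of these trials, so it offers almost no protection here.

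**The case against.** The strongest reply is that the detailed text already limits the phrase. Section 8.6.1 repeats the 0.025 statement under the primary endpoint heading, directly before the primary decision rule, and Section 8.8 opens by naming the primary endpoint. Section 8.1 is only a summary, and its Multiplicity row openly says the two components are adjusted for the interim alone. That makes the narrow meaning the likely intention. But it supports bringing Section 8.1 into line; it does not make the unrestricted sentence correct. The Multiplicity row also speaks only of the first family and does not say that the second has its own full level.

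A second reply is that the disputed clause in Section 8.8 concerns the second family alone, where error is indeed held. That is fair on a narrow reading. However, the clause uses the term study-wise, which in Section 8.1 follows a list of all the tests.

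Third, a split or link might be drawn in Figure 2. This cannot be excluded, so the finding is limited to the text and the fix allows for it.

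Fourth, the excess is small and model-dependent. This stands. At HR 0.90 on HF hospitalization only there is no excess, and for CV death only it largely disappears when an interim stop is taken. Section 8.7.2 does allow the interim to be cancelled if events accrue much faster than expected.

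**Conclusion.** The concern holds as a minor point. On the text as written, one-sided 0.025 is controlled for the primary endpoint and within each secondary family behind the primary gate, but not across both families.

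The firm case is benefit on HF hospitalization only. The chance of a false CV death or all-cause mortality claim is then about 2.9% to 3.3% at HR 0.80, an excess of 0.4 to 0.8 points, and up to about 3.7% at HR 0.60. For benefit on CV death only, the excess appears mainly if the trial runs to the final analysis. These are ranges over the scenarios examined, not strict bounds. They depend on the assumed frailty, non-CV death rate and independence of the components. The qualitative conclusion needs only that the two nulls sit in separate families with open gates and are not perfectly correlated.

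**What to change.** In the error-rate sentence of Section 8.1, and in the second-family sentence of Section 8.8, state that one-sided 0.025 is controlled for the primary endpoint and within each secondary family after a significant primary, but not jointly across the two families. Report secondary claims on that basis. If Figure 2 does contain a split or link between the families, describe it in the text of Section 8.8 instead.

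Section 8.6.1 needs no change. The cost is two sentences of wording; alpha levels, gates, test order, power and sample size stay as they are.
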